Overview of Study Design: Patients will undergo standard of care ASCT with conditioning regimen determined by the treating physician per institutional guidelines. The ASCT is not considered part of this study. Consolidation therapy will begin on between Day 80 and Day 120 following ASCT and will consist of four 28-day cycles of IRD (ixazomib, lenalidomide, & dexamethasone). Barring dose modifications for toxicity, 4 mg of ixazomib and 40 mg of dexamethasone will be administered on Days 1, 8, and 15, and 15 mg of lenalidomide will be administered on daily on Days 1-21. Following completion of consolidation therapy, patients will undergo restaging and will be randomized on a 1:1 basis to maintenance therapy with ixazomib or lenalidomide. Patients will be stratified based on MRD status at restaging (MRD-positive v. MRD-negative). Barring dose modifications for toxicity, ixazomib maintenance will consist of 4 mg administered on Days 1, 8 and 15 of each 28-day cycle, and lenalidomide maintenance will consist of 10 mg daily on Days 1-28 for the first three 28-day cycles and 15 mg daily for all further cycles. Maintenance therapy with either ixazomib or lenalidomide will continue until the patient experiences disease progression or unacceptable toxicity.
Study Population: Patients between the ages of 18 and 70 years of age (inclusive) at time of enrollment with a histologically confirmed diagnosis of symptomatic multiple myeloma, who have received at least two cycles of any regimen as initial systemic therapy for multiple myeloma and are within 2-16 months of the first dose of initial therapy who provide voluntary written consent.
Duration of Study: Three years to complete accrual; approximately 7 year patient participation; therefore 10 years total.

Table of Contents

STUDY SCHEMA.....	7
PROTOCOL SUMMARY	8
LIST OF ABBREVIATIONS AND GLOSSARY OF TERMS	11
1.0 BACKGROUND AND RATIONALE.....	13
1.1 Multiple Myeloma.....	13
1.2 Ixazomib (MLN9708).....	13
1.3 Value of Minimal Residual Disease Assessment.....	24
1.4 Study Rationale	25
1.5 Correlative Studies Background.....	26
2.0 OBJECTIVES	26
2.1 Primary Objective	26
2.2 Secondary Objectives.....	26
2.3 Exploratory Objectives.....	26
3.0 PATIENT SELECTION	27
3.1 Inclusion Criteria.....	27
3.2 Exclusion Criteria.....	28
3.3 Inclusion of Women and Minorities.....	29
4.0 REGISTRATION PROCEDURES	29
4.1 Confirmation of Patient Eligibility.....	29
4.2 Patient Registration in the Siteman Cancer Center Database	29

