3.0 PATIENT SELECTION

3.1 Inclusion Criteria

Each patient must meet all of the following inclusion criteria to begin IRD Consolidation

1. Between the ages of 18 and 70 years of age (inclusive) at time of enrollment
2. Voluntary written consent must be given before performance of any study-related procedure not part of standard medical care, with the understanding that consent may be withdrawn by the patient at any time without prejudice to future medical care.
3. Histologically confirmed diagnosis of symptomatic multiple myeloma. (Patients with multiple myeloma with secondary amyloidosis are eligible.)
4. Received at least two cycles of any regimen as initial systemic therapy for multiple myeloma and are within 2-16 months of the first dose of initial therapy
5. Eastern Cooperative Oncology Group (ECOG) performance status and/or other performance status 0, 1, or 2 (see Appendix A).
6. Adequate organ function as defined below:
 - Absolute neutrophil count (ANC) $\geq 1,000/\text{mm}^3$.
 - Platelet count $\geq 75,000/\text{mm}^3$; platelet transfusions to help patients meet eligibility criteria are not allowed within 7 days before study enrollment.
 - Total bilirubin $\leq 1.5 \times$ the upper limit of the normal range (ULN).
 - Alanine aminotransferase (ALT) and aspartate aminotransferase (AST) $\leq 3 \times$ ULN.
 - Calculated creatinine clearance ≥ 30 mL/min (see Appendix B).
7. Women of childbearing potential (as defined in Section 5.6) must follow pregnancy testing requirements as outlined in the Revlimid REMS® program material. This is defined as either committing to continued abstinence from heterosexual intercourse or beginning TWO acceptable methods of contraception (one highly effective method and one additional effective method (as defined in Section 5.6) AT THE SAME TIME) at least 28 days prior to the start of lenalidomide, for the duration of study participation, and for 28 days following the last dose of lenalidomide. Women of childbearing potential must also agree to ongoing pregnancy testing.
8. Men must agree to use a latex condom during sexual contact with a woman of childbearing potential even if they have had a successful vasectomy. All patients must be counseled at a minimum of every 28 days about pregnancy precautions and risks of fetal exposure. Should a woman become pregnant or suspect she is pregnant while participating in this study, she must inform her treating physician immediately.

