A woman of childbearing potential is defined as a sexually mature woman who: 1) has not undergone a hysterectomy or bilateral oophorectomy or 2) has not been naturally postmenopausal for at least 24 consecutive months. Women of childbearing potential are required to have a negative serum or urine pregnancy test within 10-14 days prior to and again no more than 24 hours before the first dose of lenalidomide. Women of childbearing potential are required to use two forms of contraception at the same time, including one highly effective method (i.e., intrauterine device, hormonal (birth control pills, injections, or implants), tubal ligation, partner's vasectomy) and one additional effective (barrier) method (i.e., latex condom, diaphragm, cervical cap), from the time of signing of the informed consent form through 90 days after the last dose of study drug. Male patients engaged in a sexual relationship with a woman of childbearing potential must agree to use a latex condom during sexual contact, even if he has had a successful vasectomy.

If a patient is suspected to be pregnant, both study drugs should be immediately discontinued. In addition a positive urine test must be confirmed by a serum pregnancy test. If it is confirmed that the patient is not pregnant, the patient may resume dosing.

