5.7 Duration of Therapy

If at any time the constraints of this protocol are considered to be detrimental to the patient's health and/or the patient no longer wishes to continue protocol therapy, the protocol therapy should be discontinued and the reason(s) for discontinuation documented in the case report forms.

Patients will be removed from the study for any of the following reasons:

- Disease progression or relapse
- Death
- Adverse event(s) that, in the judgment of the investigator, may cause severe or permanent harm or which rule out continuation of study drug
- General or specific changes in the patient's condition render the patient unacceptable for further treatment in the judgment of the investigator
- Suspected pregnancy
- Serious noncompliance with the study protocol
- Lost to follow-up
- Patient withdraws consent
- Investigator removes the patient from study
- The Siteman Cancer Center decides to close the study

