5.8 Duration of Follow-up

Participants will be followed for 18 months after removal from study or until death, whichever occurs first.

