8.0 STUDY CALENDAR

Please note that all assessments allow a window of +/-3 days for scheduling issues.

	Screening		Consolidation ³			Restaging ⁴	Maintenance ⁵			EOS ⁷	F/U ⁸
	Prior to ASCT ¹	Prior to beginning consolidation ²	D1	D8	D15		D1	D8	D15		
Informed consent	X										
H&P, ECOG PS, plasmacytoma assessment	X	X	X ¹³			X	X ^{13,14}			X	X ¹⁵
CBC & CMP	X		X ¹³		X ⁶	X	X ^{13,14}			X	
SPEP and immunofixation	X	X	X ¹³			X	X ^{13,14}			X	
24h urine for total protein, UPEP, and immunofixation ⁹	X	X	X ¹³			X	X ^{13,14}			X	
Serum-free light chains & β2 microglobulin	X	X	X ¹³			X	X ^{13,14}			X	
Quantitative immunoglobulins (IgA, IgG, IgM)	X	X	X ¹³			X	X ^{13,14}			X	
Serum βhCG ¹⁰	X	X	X				X			X	
Bone marrow biopsy and aspirate ¹¹	X	X				X	X ¹⁶				
Central labs ¹² (MRD Analysis)		X				X	X ¹⁶				
Central labs ¹² (Hevylite)	X		X ¹³			X	X ^{13,14}			X	
Central labs ¹⁸ (Sub-study)		X ¹⁸					X ¹⁸				
Ixazomib			X	X	X		X	X	X		
Lenalidomide			Days 1-21				Days 1-28				
Dexamethasone			X	X	X						
Administration Questionnaire ¹⁷			X				X				
Adverse events assessment			X ----- X								

1. Day -60 to Day -2

2. Day +80 to Day +120; to occur within 28 days prior to C1D1 of consolidation

3. 4 28-day cycles

4. Prior to beginning maintenance (approx. Day +192 to Day +232); to occur within 28 days after completing C4 of consolidation and within 28 days prior to C1D1 of maintenance

5. 28-day cycles; continued until progression or unacceptable toxicity

6. Cycles 1-2 only

7. Within 30 days of last dose of study drug(s)

8. Every 3 months for 18 months

9. Repeat 24h urine only required for patients with ≥ 200 mg/24h of M-protein at screening

10. Women of childbearing potential only; 2 negative tests are required within 14 days before study drug dosing on C1D1 of consolidation

11. Bone marrow aspirate and core biopsy – differential required; Cytogenetics, and fluorescent *in situ* hybridization (FISH) studies performed per institutional guidelines.

12. See Section 9.0

13. Not required on C1D1 if screening/restaging visit occurred within 28 days prior

14. C1-C4 then every 3 cycles thereafter (i.e., C7, C10, C13 ...)

15. A telephone call to assess OS and PFS can be made in lieu of a physical exam

16. Cycle 13 for all patients. Cycle 25 and 37 also required for patients in suspected or confirmed CR/sCR at that time.

17. See Appendix D. Patient to complete following each cycle of study treatment (consolidation and maintenance).

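### Section 5.6 lets a woman resume dosing once pregnancy is ruled out, but 5.7 removes her on suspicion alone; 11.9 tells her to stop bortezomib, which is not a study drug

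*Combined protocol and SAP*

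**What the plan says.** Section 5.6 (Pregnancy Risks) sets a procedure. On suspicion of pregnancy, study drug stops at once. Then "a positive urine test must be confirmed by a serum pregnancy test". The procedure ends with a route back to treatment: "If it is confirmed that the patient is not pregnant, the patient may resume dosing".

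Section 5.7 (Duration of Therapy) opens its list with "Patients will be removed from the study for any of the following reasons". One entry is simply "Suspected pregnancy". It is not qualified by a test result or by investigator judgement, and it does not refer to 5.6. Two other entries, on adverse events and on changes in the patient's condition, do leave the decision to the investigator.

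Section 5.8 states what follows removal: "Participants will be followed for 18 months after removal from study or until death, whichever occurs first".

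Section 11.9 (Reporting to Millennium) instructs a woman who is pregnant, or suspects that she is, to tell the investigator and to discontinue bortezomib permanently. Section 5.1 gives the trial treatment as ixazomib, lenalidomide and dexamethasone in consolidation, and ixazomib or lenalidomide in maintenance.

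On menopause, the list of acceptable female patients in 5.6 includes those at least 1 year postmenopausal. The definition of childbearing potential later in 5.6 uses 24 consecutive months. Its two limbs, one surgical and one menopausal, are joined by 'or'.

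**The concern.** The two sections give opposite instructions for the same event. A site following 5.6 holds drug, tests and restarts. A site following 5.7 takes the patient off study before or despite a negative test. A woman who is not pregnant could then lose myeloma treatment that the protocol elsewhere says she may resume, and different sites could handle the same situation differently.

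There is also a small analysis consequence. Section 15.3 restricts the consolidation efficacy analysis to patients who complete four cycles, so a wrongful removal in consolidation drops the patient from the primary comparison. In maintenance the analysis is by intent to treat, so she stays in the set, but off therapy and on the shorter follow-up schedule.

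The instruction in 11.9 is an error of a different kind. It sits where sites look when reporting a pregnancy, and read literally it stops nothing the patient is taking.

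**Working it through.** The plan states no figure on this point, so the check is to run the same cases through each section.

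| Case | 5.6 | 5.7 | 11.9 |
|---|---|---|---|
| Pregnancy suspected, result pending | Stop drug, test | Remove from study | Stop bortezomib permanently |
| Suspected, then ruled out | May resume | Removed; no exception | Stop bortezomib permanently |
| Suspected, then confirmed | Stays off drug (no route to resume) | Removed | Stop bortezomib permanently |

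**5.6 against 5.7.** They agree when pregnancy is confirmed. They conflict when it is ruled out: one section permits resumption, the other requires removal. Both take the patient off drug on suspicion, so the conflict concerns only what happens after a negative test.

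**11.9.** Bortezomib is not among the drugs in 5.1, so the instruction has no effect on any study drug. It also demands permanence on suspicion alone. Simply putting the name of a study drug in its place would therefore create a new conflict with the right to resume in 5.6, so the whole clause needs rewording.

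**Effect on the analysis sets.**
- Removed in consolidation: fewer than four cycles completed, so outside the efficacy set of 15.3.
- Removed in maintenance: still in the intent-to-treat set, therapy ended, 18 months of follow-up under 5.8.
- Scale: section 15.0 plans about 240 patients to obtain 220 evaluable, an allowance of 240 − 220 = 20. If evaluable means the efficacy set of 15.3, each wrongful removal in consolidation uses one of those 20. The documents give no expected number of such removals.

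**Menopause thresholds.** With the two limbs of the definition read as 'and', the 5.6 list and the 5.6 definition differ for women 12 to under 24 months after menopause who are not surgically sterile: 24 − 12 = 12 months. Read literally with 'or', any woman without hysterectomy or oophorectomy counts as of childbearing potential however long after menopause, so the band has no upper limit.

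**The case against.** The best defence is that 5.6 is the specific procedure and 5.7 a general list, so a sensible site would apply 5.6. The calendar in section 8.0 also schedules serum pregnancy tests on Day 1 in both phases for women of childbearing potential, so a doubt can be settled quickly. This reading is plausible, but nothing in the documents states it, and the lead-in to 5.7 is mandatory. What stands is that fetal safety is protected on either reading, because both sections stop drug at once. The same holds for 11.9: the wrong drug name does not leave a pregnant woman on treatment.

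A reader might infer more than the documents support in four places.

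- **That the patient's own suspicion triggers removal.** Criterion 8 in 3.1 says "Should a woman become pregnant or suspect she is pregnant while participating in this study, she must inform her treating physician immediately". That is a duty to tell her physician. It does not make her report a reportable event in the sense of section 11, and nothing equates it with the removal reason in 5.7.
- **That PFS and OS follow-up would shrink from about seven years to about two.** The protocol summary's "approximately 7 year patient participation" is an overall estimate, not promised follow-up from transplant. Nor is the start of maintenance fixed by the calendar entry "Prior to beginning maintenance (approx. Day +192 to Day +232", which belongs to restaging. Note 4 allows restaging up to 28 days after cycle 4 and maintenance up to 28 days after restaging, so maintenance could start as late as about Day 232 + 28 + 28 = 288 without any dose delay. The 18-month limit also applies to removal for any reason.
- **That women 12 to under 24 months after menopause would go without contraception.** Criterion 7 applies the 5.6 definition of childbearing potential to two-method contraception (or abstinence) as well as to testing, and criterion 9 binds every participant to the lenalidomide REMS programme. This largely closes the gap at entry, and a site that follows the stricter definition satisfies both rules.
- **That the 28 days of contraception after treatment in criterion 7 contradict the 90 days in 5.6.** The first runs from the last lenalidomide dose and the second from the last study drug dose. Both can be met together.

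**Conclusion.** The conflict between 5.6 and 5.7 is real on the current text, and the drug named in 11.9 is wrong. Both are operative instructions and should be corrected. The harm is confined to a woman whose suspected pregnancy is ruled out: wrongful removal, with loss of her place in the efficacy set if it happens in consolidation, or loss of therapy and a move to 18-month follow-up if it happens in maintenance. The two menopause thresholds and the 'or' in the definition are minor alignment points.

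That few patients are likely to be affected is a judgement, since the documents give no count. No power or sample size figure changes. The conclusion assumes that the removal list in 5.7 means what it says; if the sponsor intends 5.6 to prevail, the text should state it.

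**What to change.** 1. In 5.7, replace the suspected-pregnancy entry with: *Confirmed pregnancy (if suspected, follow Section 5.6)*. The immediate hold, the serum test and resumption only if not pregnant stay as they are in 5.6.
2. In 11.9, replace the bortezomib clause with: *must hold all study drugs immediately and, if pregnancy is confirmed, permanently discontinue all study drugs*.
3. As minor alignment in 5.6, change the 1-year threshold in the list to 24 consecutive months and join the two limbs of the childbearing-potential definition with 'and'.

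The cost is an amendment to the wording of 5.6, 5.7 and 11.9. No visit, test, sample size or analysis changes, and protection is not weakened because drug still stops on suspicion.

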5.7 Duration of Therapy

If at any time the constraints of this protocol are considered to be detrimental to the patient's health and/or the patient no longer wishes to continue protocol therapy, the protocol therapy should be discontinued and the reason(s) for discontinuation documented in the case report forms.

Patients will be removed from the study for any of the following reasons:

- Disease progression or relapse
- Death
- Adverse event(s) that, in the judgment of the investigator, may cause severe or permanent harm or which rule out continuation of study drug
- General or specific changes in the patient's condition render the patient unacceptable for further treatment in the judgment of the investigator
- Suspected pregnancy
- Serious noncompliance with the study protocol
- Lost to follow-up
- Patient withdraws consent
- Investigator removes the patient from study
- The Siteman Cancer Center decides to close the study

5.8 Duration of Follow-up

Participants will be followed for 18 months after removal from study or until death, whichever occurs first.

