10.0 DATA SUBMISSION SCHEDULE

Case report forms with appropriate source documentation will be completed according to the schedule listed in this section. Electronic data management systems will be used in this trial in collaboration with the Division of Biostatistics at Washington University.

REDCap is a web-based clinical studies data management system that will be used for capture of clinical data from this trial. The case report forms developed for this trial will be transformed to electronic format. An electronic study calendar will drive the study's data collection workflow.

Each participating center has access only to data from its own participants. Washington University, as the data coordinating center, has access to data from all sites. Training in entering data in REDCap is required before a participating center will be given access to the database. In addition, a participating center must have IRB approval of this protocol prior to initiation of REDCap data entry training, which must be completed prior to site study activation.

Case Report Form	Submission Schedule
Original Consent Form	Prior to registration
Registration Form Eligibility Form Medical History Form Treatment History Form Safety Labs Form MM labs Form Stem Cell Transplant Form	At Baseline
Study Drug Dosing Form Safety Labs Form MM Labs Form Response Form	Each Cycle of Treatment
Bone Marrow Form Response Form	As Per Protocol Requirements
Correlative Studies Form	As Per Protocol Requirements
Adverse Events	Continuous from baseline through safety follow-up visit
MedWatch Form	See Section 8.0 for reporting requirements

Any queries generated by Washington University must be responded to within 28 days of receipt by the participating site. The Washington University research team will conduct a regular review of data status at all secondary sites, with appropriate corrective action to be requested as needed.

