15.3 Data Analysis

For the analysis of consolidation therapy, the data for safety analysis will include these patients who have at least 1 dose of IRD consolidation therapy, while the data for efficacy analysis will include patients who complete 4 cycles therapy. Demographic and clinical characteristics of the sample, as well as adverse events, complications and loss to follow-up will be summarized using descriptive statistics. The change of MRD-negative rates for pre- and post-consolidation therapy will be described using contingency table and compared by McNemar test. The incidences of mortality, progression, relapse, as well as tumor response (complete response and overall) and their 95% confidence intervals following consolidation therapy will also be calculated.

Data analysis for maintenance portion will be performed following the intent-to-treat (ITT) principle. The balance of demographic and baseline clinical characteristics between two arms will be compared using t-test, Mann-Whitney rank-sum test, or Chi-square test as appropriate. The distributions of responses and adverse events across two arms will be summarized using contingency tables and compared by 2-sample Chi-square test or Fisher's exact test. Contingency table and Fisher's exact test will also be used to assess the between-arms difference for the rates of conversion from MRD-positive to MRD-negative. Chi-square test will be used to compare the distribution of responses, and Kaplan-Meier curves with log rank tests will be used to compare PFS and OS.

Overall survival (OS) will be defined as time from ASCT to death due to any causes, and survivors will be censored at withdrawal or study closeout. Progression-free survival (PFS) will be defined as time from ASCT to progression, relapse, or death, whichever occurs first, and those event-free survivors will be censored at withdrawal or study closeout. The between-arm differences in OS and PFS will be described using Kaplan-Meier product limit estimator and compared by log-rank tests. Kaplan-Meier curves will also be used to describe the association between MRD status (both prior to and after consolidation therapy) and OS or PFS, and proportional hazards Cox models will be used to control the potential confounding effects of other patient and clinical characteristics.

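### OS survivors are censored at withdrawal or closeout, but scheduled contact with progressors ends 18 months after removal, so late OS would be overstated

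*Combined protocol and SAP*

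**What the plan says.** - **Removal.** Section 5.7 lists "Disease progression or relapse" first among the reasons for taking a patient off study.
- **Contact after removal.** Section 5.8: "Participants will be followed for 18 months after removal from study or until death, whichever occurs first". Calendar note 8 (section 8.0) gives the schedule: "Every 3 months for 18 months". Note 15 belongs to the same follow-up column: "A telephone call to assess OS and PFS can be made in lieu of a physical exam".
- **OS censoring.** Section 15.3 counts OS from ASCT to death from any cause, and "survivors will be censored at withdrawal or study closeout".
- **Time scale.** The Protocol Summary plans three years of accrual plus about seven years of participation, ten in total.
- **Use of OS.** OS of IRD consolidation, and OS by MRD status, are secondary objectives (2.2). Section 15.3 plans Kaplan-Meier curves, log-rank tests and Cox models for OS.
- **New malignancies.** Section 11.9 asks for new primary malignancies to be reported for at least three years after the last dose of the investigational product. Section 11.10 ends adverse event collection at the end of study visit.

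**The concern.** The censoring rule and the follow-up schedule do not fit together. A patient who progresses two years after ASCT has scheduled contact to about year 3.5, while closeout lies several years later. For a progressor still alive when contact ends, 15.3 names a censoring date on which nobody is scheduled to know whether the patient is alive.

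Either way of handling that patient biases OS upward. Carrying the patient to closeout turns unseen deaths into survival time. Censoring when contact ends removes surviving progressors from the risk set while progression-free patients, who continue maintenance visits, stay in it. Kaplan-Meier assumes that censored patients have the same future risk as those still followed, and here they do not.

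At stake are the late part of the OS curve and the number of deaths available to the OS models, in a study meant to generate hypotheses for a phase III trial (1.4).

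**Working it through.** **Inputs from the documents.** Study length: 3 + 7 = 10 years, which agrees with the Protocol Summary. Contact after removal: 1.5 years (5.8). Evaluable patients: 220 (15.0). Five-year event rate on lenalidomide: about 54% (15.1). I use that rate for PFS as an illustration only; its events are progression or second-line treatment, and its time origin is not stated. HR 1.3 is the margin in 15.1.

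**Assumptions not in the documents.** Median survival after progression is 2 to 6 years (example: 3), with constant hazard unless stated. 5% of PFS events are deaths. Progression is the only cause of removal modelled.

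**Rates for the example.** λ = −ln(0.46)/5 = 0.1553 per year for PFS. μ = ln 2/3 = 0.2310 per year after progression. λ/(μ − λ) = 2.050.

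**1. True OS at 5 years.** S(5) = e^(−5λ) + 0.95 × 2.050 × (e^(−5λ) − e^(−5μ)) = 0.46 + 0.95 × 2.050 × (0.460 − 0.315) = 0.742.

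**2. Carried to closeout.** Add the deaths before year 5 that come more than 1.5 years after progression:

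U(5) = 0.95 × {e^(−1.5μ)(1 − e^(−3.5λ)) − 2.050 × e^(−5μ) × (e^(3.5(μ−λ)) − 1)} = 0.95 × {0.707 × 0.419 − 2.050 × 0.315 × 0.304} = 0.095.

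Reported OS is 0.838.

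**3. Censored when contact ends.** After year 1.5 the ratio of progressors to progression-free patients in the risk set is constant: R = 0.95 × 2.050 × (1 − e^(−1.5(μ−λ))) = 0.209. The observed death hazard is (0.05λ + μR)/(1 + R) = (0.0078 + 0.0483)/1.209 = 0.0464 per year. With S(1.5) = 0.958, reported OS is 0.958 × e^(−0.0464 × 3.5) = 0.814.

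**4. Deaths by year 7.** The same formulas give 220 × (1 − 0.607) ≈ 86 deaths and 220 × 0.186 ≈ 41 unseen, so about 45 are observed.

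**5. Other medians, constant hazard, 5-year OS** (excess from unrounded values):

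| Median after progression | True | Contact end (excess) | Closeout (excess) |
|---|---|---|---|
| 2 years | 67.8% | 75.9% (8.1) | 78.5% (10.7) |
| 3 years | 74.2% | 81.4% (7.2) | 83.8% (9.5) |
| 6 years | 83.5% | 88.3% (4.7) | 90.0% (6.4) |

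**6. Wider range by simulation.** There were 40 settings of 300,000 patients: medians 2, 3, 4, 5 and 6 years; Weibull shapes 0.5, 0.7, 1 and 1.5; and PFS either exponential or piecewise through the protocol's 13%, 25% and 54% at 1, 2 and 5 years.

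| Excess in OS | Contact end | Closeout |
|---|---|---|
| 3 years, all shapes | 0.5 to 3.4 points | 0.9 to 3.9 points |
| 5 years, constant hazard | 4.5 to 8.1 points | 6.2 to 10.7 points |
| 5 years, all shapes | 1.9 to 12.8 points | 4.1 to 15.4 points |

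Depending on the setting, 25% to 66% of deaths by year 7 go unobserved. The upper ends of the 5-year excess need a rising hazard and a median of 2 to 3 years.

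**7. Between-arm OS HR** (PFS HR 1.3, seven years). With full follow-up it is 1.21 to 1.28. Contact-end censoring changes it by −0.01 to +0.05. The closeout reading lowers it by 0.03 to 0.09. In the example the three values are 1.244, 1.268 and 1.181.

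**8. Malignancy window.** Months covered of 36 = min(36, gap + 18), where gap is the time from last ixazomib dose to removal. Gaps of 0, 6, 12 and 18 months give 18, 24, 30 and 36.

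**The case against.** The best defence is that limited follow-up after progression is a resource choice in a phase II trial with an MRD primary endpoint. OS is a secondary outcome, estimated for consolidation without a control or threshold, and no 5-year or 7-year OS is a named endpoint. A sensible analyst would not credit survival time with no contact behind it, and sites may hear of later deaths informally. The size of the bias rests almost wholly on assumptions.

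Much of this stands. The closeout reading is the less natural practice, so the contact-end figures should carry the point. It does not remove the problem, because contact-end censoring biases late OS in the same direction in every setting tried. Informal knowledge of deaths is not part of the plan, and uneven ascertainment would bring its own difficulty.

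A reader might infer more than the documents support:

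- **That removal at progression is itself the censoring date.** Section 5.7 lists withdrawal of consent as a separate reason, and note 15 assesses OS after removal.
- **That PFS should be censored at the last disease assessment.** The PFS rule, "those event-free survivors will be censored at withdrawal or study closeout", shares the closeout wording. But the follow-up column schedules no myeloma laboratory tests, so that change could discard the follow-up contacts. No PFS change is proposed here.
- **That survival is not recorded at all, because section 10.0 lists no survival form.** That list also omits other forms the protocol uses, such as the randomization form, and the calendar does schedule OS and PFS follow-up to month 18.

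**Conclusion.** The point holds for late OS. Sections 5.7, 5.8 and 15.3, read together, give an OS curve that is too high beyond about three years. With constant hazard after progression, the 5-year excess is about 5 to 8 points if patients are censored when contact ends and about 6 to 11 if they are carried to closeout. These sizes depend on the assumed survival after progression, the 5% share of deaths and the borrowed 54% event rate. The direction does not depend on which of the two censoring readings is taken.

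The limits matter as well. The primary MRD endpoint is unaffected, and OS to three years is little changed. A reader might conclude that the comparison of maintenance arms is badly distorted. Under contact-end censoring the HR moves little; only the closeout reading pulls it noticeably toward 1.

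The malignancy question is separate and minor. Scheduled contact can fall up to 18 months short of the three-year window when the last ixazomib dose is close to removal, which mainly means ixazomib-arm patients or early removals. This takes the investigational product to be ixazomib, as 7.1.2 suggests. Lenalidomide-arm patients without crossover who are removed 18 or more months after consolidation are covered by the scheduled contacts. The duty in 11.9 stands in any case; what is missing is a scheduled contact that serves it throughout.

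**What to change.** 1. In 15.3, censor OS at the date last known alive.
2. In 5.8 and calendar notes 8 and 15, add vital-status collection by telephone or record check after month 18, until death, withdrawal of consent or closeout. This could be every 6 months, or a sweep before each OS analysis.
3. Make a catch-up vital-status check for any patient already past month 18.
4. Ask about new primary malignancies at the same contacts, and reconcile 5.8, 11.9 and 11.10.

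Changing the censoring date alone is not enough: without later vital status it only selects the contact-end bias over the larger one.

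The cost is a multi-site amendment with local IRB submission (16.0), possible re-consent, and extra calls or record checks within the planned ten years. No new procedures are needed.
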